Total number of patients	
One-hundred and forty-seven (147) individuals will be randomly assigned to one of two groups; traditional physical therapy or AposTherapy on a 1:2 ratio (49:98).
 
A sample size of 147 will yield 80% power to detect an expected difference on the WOMAC pain scale, with components measured on VAS scales from 0 to 10 and a summary score standardized to also range from 0 to 10, of 1.5 at a 2-sided alpha of 0.05. The difference corresponds to a clinically meaningful moderate effect size of 0.4 standard deviation units assuming a typical standard deviation of 2.65. Anticipating an attrition rate of 10%, we aim at recruiting 162 patients for the trial.

Study groups	
Patients will be randomly assigned to one of the following groups:
 
 • Patients with knee OA treated with AposTherapy • Patients with knee OA treated with traditional physical therapy
Assessment time points	
Patients will be enrolled in the study and have clinical evaluations at the following time points:
 
 • Pre-treatment • 4 weeks following treatment initiation

- 8 weeks following treatment initiation
- 12 weeks following treatment initiation
- 24 weeks following treatment initiation
- 52 weeks following treatment initiation

**The effect of AposTherapy on pain and function in Knee Osteoarthritis (OA) population. A
randomized controlled trial**

1. Background

AposTherapy is a home-based exercise program utilizing footwear that causes exercise with normal daily activity that may significantly improve function in patients with knee pain in general, and specifically knee osteoarthritis (OA). Capitalizing on the reported excellent adherence and clinical benefit of Apos Therapy in patients with significant lower limb arthritis, we propose to evaluate this as a conservative treatment that may supplant/supplement traditional pain medications and physical therapy in knee OA population. [3-6]

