4.3. Randomization

Blocked randomization will be used to assign to their respective treatment arm. The assigning ratio will be one to two; The random method of selection will be through a computerized random number generator. The on-site coordinator will be responsible for entering and maintaining the subject randomization information.

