4.6. Sample size

Our target recruitment is 147 individuals randomly assigned to one of two groups; traditional physical therapy or AposTherapy, on a 1:2 ratio. A sample size of 147 patients will yield 80% power to detect an expected difference on the WOMAC pain scale, with components measured on VAS scales from 0 to 10 and a summary score standardized to also range from 0 to 10, of 1.5 at a 2-sided alpha of 0.05. The difference corresponds to a

[figure not shown]
clinically meaningful moderate effect size of 0.4 standard deviation units assuming a typical standard deviation of 2.65. Anticipating an attrition rate of 10%, we aim at recruiting 162 patients for the trial (54 patients will be assigned to traditional physical therapy and 108 patients will be assigned to AposTherapy)

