4.9. Outcome measures

Primary study outcome:

- Western Ontario and McMaster Universities (WOMAC) pain scale at one year.
- WOMAC function scale at one year

Secondary study outcome: at: Pre-treatment, 4 weeks, 8 weeks, 12 weeks, 24 weeks, 52 weeks.

- WOMAC pain and function subscale
- PROMIS Pain Interference and Physical Function
- Costs: Assessment of total utilization and cost from resource utilization monitored via the CMO
- MOS item of the Short Form (SF)-36
- Spatio-temporal gait assessment including gait velocity, step length, single limb support and limb symmetry measured by Zeno Walkway ®
- 6-min walk test
- Blood pressure and resting heart rate

- Treatment adherence: Measured via attendance at sessions of therapy (conventional therapy), hours of use of AposTherapy (Patient to have step counter)
- Overall activity and sleep patterns (both arms (via FitBit Charge HR (<http://www.fitbit.com/chargehr#i.f9n1ye1ehxd30p>) motion sensor worn for one week after each evaluation session, mailed back via prepaid mailer at the end of the week.)

5. Statistical analysis

All demographic data will be reported as mean standard deviations and average. Data from primary and secondary outcome measures will be checked for skewness using Fisher-Pearson coefficient of skewness. ANOVA or Kuskal-Wallis test will be applied depending on normality of data. All statistical analysis will be conducted using IBM SPSS Statistics Ver.24.

6. Benefits

- Participants will all have physical therapy for their knee
- AposTherapy involves fewer visits to the physical therapy center thus allowing individuals more time at home and lower transportation costs
- AposTherapy is done at home and more convenient
- AposTherapy will be provided for free for participants.

7. Risks

- Muscle soreness associated with exercise
- Minimal fall risk with use of new footwear device and exercise

8. Subject Reimbursement

Participants will be reimbursed a total of \$40 at each assessment point (pre-treatment, at 4 weeks, 8 weeks, 12 weeks, 24 weeks and 52 weeks after entry into the study). Participants will

receive \$95 reimbursement for their time at the completion of the study after return of all devices and materials. This will apply to all arms of the study.

Study schedule:

Study Periods	Screening	1	2	3	4	5	6	7
Visit		1	2	3	4	5	6	7
Time (week)	-2	0	4	8	12	24	52	
Patient Information and Informed Consent	X							
Demographics	X							
Medical History	X							

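### With 1:2 allocation, Section 5 should prespecify an unequal-variance (Welch) comparison instead of ordinary ANOVA, whose 5% error rate depends on the two arms having equal SDs

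*Combined protocol and SAP*

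**What the plan says.** Section 5 checks the primary and secondary outcomes with the Fisher-Pearson skewness coefficient and then states that "ANOVA or Kuskal-Wallis test will be applied depending on normality of data". It names no Welch or robust-variance version, no check of variances, no covariates and no confidence intervals.

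The allocation is unequal. The synopsis assigns patients to "traditional physical therapy or AposTherapy on a 1:2 ratio (49:98", and Section 4.3 repeats that "The assigning ratio will be one to two".

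The error rate appears only in the sample size text. Section 4.6 specifies a difference "of 1.5 at a 2-sided alpha of 0.05", "assuming a typical standard deviation of 2.65". That one SD serves both arms. The primary outcomes in Section 4.9 are WOMAC pain and WOMAC function at one year.

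**The concern.** With two groups, ordinary ANOVA is the equal-variance t-test (F = t²). Its standard error comes from a pooled variance that weights each arm by its degrees of freedom. At 49:98 the AposTherapy arm supplies 97/145 = 67% of that weight and physical therapy 48/145 = 33%. The true variance of the difference in means is the sum of each arm's variance divided by its size, so a given variance counts twice as much in the arm of 49 as in the arm of 98. The two weightings run in opposite directions.

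If physical therapy outcomes are the more variable, the pooled standard error is too small and false positives exceed 5%. If AposTherapy outcomes are the more variable, it is too large and the test becomes conservative and loses power. At 1:1 the discrepancy nearly vanishes, so the exposure comes from the trial's own allocation.

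The planned check does not guard against this. Skewness describes asymmetry; two symmetric distributions can have very different spreads. A skewed result sends the analysis to Kruskal-Wallis, which is also disturbed by unequal spread, though less.

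Equal spread cannot be taken for granted. Section 4.7 compares a course of clinic sessions lasting 4 to 8 weeks with an individually calibrated home device used for a year. If benefit varies between patients more under one treatment than the other, the SDs will differ even where the means do not.

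**Working it through.** **The plan's own figure.** Section 4.6 says "A sample size of 147 patients will yield 80% power to detect an expected difference on the WOMAC pain scale". This does not reproduce. 1.5/2.65 is 0.566 SD, not the stated 0.4 SD. At 49:98 and two-sided 5%, 1.5 points with SD 2.65 gives 89.9% power (89.5% by noncentral t), and 0.4 SD gives 62.8% (62.2%). That is a separate issue. What matters here is the two-sided 0.05 in the same sentence and whether the planned test delivers it.

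**Inputs.** From the documents: arm sizes 49 and 98, and two-sided alpha 0.05. Assumed: the ratio r = SD(physical therapy)/SD(AposTherapy), shown from 0.5 to 2 because the documents give no value; normal data; equal true means.

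**Formula.** Set the AposTherapy SD to 1.

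- Pooled variance = (48r² + 97)/145.
- Squared standard error used by ANOVA = pooled variance × (1/49 + 1/98).
- True squared standard error = r²/49 + 1/98.
- k = square root of (ANOVA value / true value).
- Large-sample type I error = 2 × (1 − Φ(1.96k)).

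**r = 1.5.** Pooled variance = (48 × 2.25 + 97)/145 = 1.414. ANOVA uses 1.414 × 0.03061 = 0.0433. The true value is 2.25/49 + 1/98 = 0.0561. So k = √(0.0433/0.0561) = 0.878, and the error is 2 × (1 − Φ(1.721)) = 8.5%.

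**r = 0.67.** Pooled variance = (48 × 0.444 + 97)/145 = 0.816. ANOVA uses 0.0250 and the true value is 0.0193. So k = 1.138 and the error is 2.6%.

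**Simulation.** 200,000 trials per setting for ANOVA and Welch at 49:98, 40,000 for Kruskal-Wallis and 100,000 for the 74:73 comparison:

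| r | ANOVA, formula | ANOVA, simulated | Kruskal-Wallis | Welch | ANOVA at 74:73 |
|---|---|---|---|---|---|
| 0.5 | 1.6% | 1.7% | 3.4% | 4.9% | 5.2% |
| 0.67 | 2.6% | 2.6% | 3.7% | 5.0% | 5.1% |
| 0.8 | 3.5% | 3.5% | 4.1% | 4.9% | 5.1% |
| 0.91 | 4.3% | 4.2% | 4.5% | 4.9% | 4.9% |
| 1.0 | 5.0% | 5.0% | 5.1% | 5.0% | 5.1% |
| 1.1 | 5.8% | 5.7% | 5.5% | 5.0% | 5.0% |
| 1.25 | 6.9% | 6.9% | 6.1% | 5.0% | 5.0% |
| 1.5 | 8.5% | 8.5% | 7.1% | 5.0% | 4.9% |
| 2.0 | 11.0% | 11.2% | 8.7% | 5.2% | 5.0% |

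Repeat runs differ by 0.1 to 0.2 points (for example 6.8% at r = 1.25 and 11.0% at r = 2.0).

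**WOMAC floor.** Scores were drawn with latent SD 2.65 and clipped to 0–10. With arm means of 4.6 and 2.7 (a difference of 1.9), r becomes about 1.11 and a pooled 95% interval covers about 94.1%. At the planned difference of 1.5 (4.6 and 3.1), r is about 1.07 and coverage is 94.6% to 94.8%. The arm means are assumptions.

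**Cost of Welch when the SDs are equal.** For 1.5 points at SD 2.65 and 49:98, simulated power is about 89.3% with pooled ANOVA and 89.1% with Welch.

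**The case against.** The strongest reply is that nothing in the documents shows the SDs will differ. They give one SD, and the ratios above are assumptions. If treatment made no difference to any patient, randomisation would give both arms the same distribution and ANOVA would hold 5%. The larger error rates need equal means together with clearly unequal spread. The obvious mechanism, compression of scores towards zero in the better arm, needs unequal means. It therefore bears on interval coverage rather than on false positives, and its effect is small. All of this stands. It makes the size of the problem conditional, but it does not give a reason to rely on equal SDs that the plan has not established.

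A reader might infer that the trial's 5% error rate is simply wrong, or wrong as soon as the SDs differ at all. The documents do not support that: a 10% difference in SD moves the error only to about 5.7% or 4.2%. A reader might also infer that the planned intervals are wrong. Section 5 plans none, so the point applies only to pooled intervals that might be reported later.

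Nor do the ANOVA figures carry over to every secondary outcome. Cost or activity data that fail the skewness check would go to Kruskal-Wallis, which has no pooled standard error and departs less from 5%. That softens the point without removing it, since Kruskal-Wallis still reaches about 7% at a ratio of 1.5.

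Finally, ordinary ANOVA is a conventional choice. That is fair, and at 1:1 there would be little to say.

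**Conclusion.** The point holds as a conditional weakness that is cheap to remove. Section 5 names a pooled-variance test under 1:2 allocation, and its only check cannot detect the condition that would invalidate the test. For SD ratios between 0.8 and 1.25, type I error lies between about 3.5% and 6.9%; at 0.67 and 1.5 it is 2.6% and 8.5%. It is liberal if physical therapy is the more variable arm and conservative if AposTherapy is. Kruskal-Wallis shows the same pattern to a lesser degree, and Welch stays between 4.9% and 5.2% over the whole range from 0.5 to 2.

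These figures rest on normal data, equal means, 49 and 98 patients analysed, and assumed SD ratios. They do not show that the primary WOMAC comparison will be materially wrong. They do show that its error rate depends on an assumption that the plan neither states nor checks.

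**What to change.** In Section 5, because allocation is 1:2, state that the between-arm analysis of WOMAC pain, WOMAC function and the other continuous outcomes is the Welch unequal-variance comparison of means, reported with its 95% confidence interval. If a baseline-adjusted model is adopted, take HC3 heteroscedasticity-robust standard errors from it instead. HC3 was not simulated here; it is the regression counterpart of the same idea.

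Apply the method without a preliminary test of variance or skewness, so that the data do not choose the primary test. Keep Kruskal-Wallis only as a sensitivity analysis. The skewness coefficient can still be reported as a description.

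This takes a sentence or two in the plan and no change to design, sample size or data collection. If the SDs turn out equal, the price is about 0.2 percentage points of power for 1.5 points at SD 2.65.

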- Total healthcare utilization and costs of physical therapy and AposTherapy will be assessed, including physical therapy, ED visits, pharmacological pain treatments, joint injections, imaging studies, surgical procedures, physician visits related to knee pain and total physician visits
- Pain medication consumption
- Quality of life
- Gait assessment
- 6-min walk test

- Blood pressure and resting heart rate
- Adherence to treatment - AposTherapy group (Patient to have step counter permanently attached to AposTherapy device)
- Overall activity and sleep patterns, both groups. Will be measured via FitBit Charge HR (<http://www.fitbit.com/chargehr#i.f9n1ye1ehxd30p>) motion sensor worn for one week after each evaluation session, mailed back via prepaid mailer at the end of that week.

4. Materials and Methods

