4.8. Assessment time points

Visits for evaluation will be done in a blinded fashion with independent evaluators who will perform all follow-up evaluations. Patients will have all outcome measures on initial entry into the study (pre-treatment), at 4 weeks, 8 weeks, 12 weeks, 24 weeks and 52 weeks after entry into the study.

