In- /Exclusion Criteria	X							
Radiography	X							
Randomization	X							
Administer traditional physical therapy		Physical Therapy is administered according to the protocol for the duration of enrollment in the study						
Administer Biomechanical Device		X						
Adjustment Biomechanical Device			X	X	X	X		
VAS and ODI		X	X	X	X	X	X	
Secondary outcome measures		X	X	X	X	X	X	
Adverse Events		X	X	X	X	X	X	

Resources

AposTherapy	Montefiore

 • Training for Montefiore PTs • Full-time Apos resource to manage program on-site at Montefiore • AposTherapy devices 	
 • Clinical Principle Investigator Lead • Research staff – 2 coordinators • Data informatics, including patient population, demographics, historical costs, etc. • Research infrastructure including IRB, recruitment, clinical expertise • Study materials • Step counter/Fitbit monitors

Staff	Salary - Rate/Hr	Fringe	FTE or Hours	Total Cost
Attending Physician Supervision	\$165,000	30.5%	0.2	\$43,065
Study coordinator	\$0	0.0%	2	\$0
These will be Everest individuals				
Informatics costs	\$75		100	\$7,500
Biostatistical support	\$150		100	\$15,000
CMO staff support	\$65,000	30.5%	0.5	\$42,413
Total Staffing Cost				\$107,978
Materials	Cost per Unit	# of Patients	Qty	Subject Costs
Step counters:				
25% of Patients and 10% loss	\$50	37	41	\$2,050
Fitbit HR Monitors:				
25% of Patients	\$150	37	41	\$6,150
Mailing to Recover step counter/Fitbit:*	\$10	37		\$14,800

Transportation costs:	\$100	147		\$14,700
Subject Complete Reimbursement	\$100	147		\$14,700
Zeno Walkway	\$20,000		1	\$20,000
Total Materials				\$72,400
Total cost of the study				\$180,378

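### The cost comparison specifies no use of pre-entry cost and, if cost is skewed, yields no mean cost difference; the loss is precision and interpretability on a secondary outcome, not bias

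*Combined protocol and SAP*

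**What the plan says.** **Outcome.** Section 3.2 makes utilisation and cost the first secondary outcome: "Total healthcare utilization and costs of physical therapy and AposTherapy will be assessed, including physical therapy, ED visits, pharmacological pain treatments, joint injections". The list continues through imaging, surgery and physician visits, both knee-related and total. Section 4.9 gives the source: "Costs: Assessment of total utilization and cost from resource utilization monitored via the CMO". Section 1 (Background) presents lower cost as one of the hoped-for advantages over physical therapy.

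**Pre-entry data.** The secondary outcomes in section 4.9, cost among them, stand under one schedule line: "Secondary study outcome: at: Pre-treatment, 4 weeks, 8 weeks, 12 weeks, 24 weeks, 52 weeks". Section 4.8 agrees: "Patients will have all outcome measures on initial entry into the study (pre-treatment". Separately, the Resources table after the study schedule lists as a site contribution "Data informatics, including patient population, demographics, historical costs, etc". No look-back period is given anywhere, and the plan does not say whether cost is to be cumulated to 52 weeks or compared visit by visit.

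**Analysis.** Section 5 has one rule for all outcomes: "Data from primary and secondary outcome measures will be checked for skewness using Fisher-Pearson coefficient of skewness", and then "ANOVA or Kuskal-Wallis test will be applied depending on normality of data". It names no covariate, change score, repeated-measures model or cost model.

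**Design.** The Synopsis plans "traditional physical therapy or AposTherapy on a 1:2 ratio (49:98" patients. Section 4.3 describes blocked randomisation and mentions no stratification.

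**The concern.** Total cost varies between patients for reasons unconnected with the allocated therapy. The outcome includes ED visits, surgery and all physician visits, so a few habitual high users can weigh heavily in a control arm of 49. A patient's cost before entry measures part of that tendency, cannot be affected by allocation, and is something the plan appears to foresee having. Leaving it out widens the interval around the cost difference.

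The fallback test raises a second difficulty. Costs of this kind are usually right-skewed, and Section 5 then leads to Kruskal-Wallis. That test compares ranks. Whether one therapy costs less is a question about the mean, because mean cost times number of patients is what is paid. A rank test can be significant when means are equal, or not significant when they differ. Arm means could be printed beside it, but the p-value would not refer to them and no interval would follow.

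Adjusting WOMAC scores for their own baseline would not help here, because cost is a different outcome from a different source.

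**Working it through.** **The plan's own figure.** There is none for cost: no SD, target difference or power. The only sample-size calculation (section 4.6) concerns WOMAC pain. From it I take only the arm sizes, 49 and 98. Results below are in units of the SD of cost.

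**1. Unadjusted precision.**
- SE = √(1/49 + 1/98) = √0.0306 = 0.175 SD.
- 95% half-width = 1.96 × 0.175 = 0.343 SD.
- Difference detectable with 80% power, two-sided 0.05 = (1.960 + 0.842) × 0.175 = 0.490 SD.

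**2. Gain from adjustment, raw-scale correlation.** Let r be the correlation between prior and follow-up cost in currency units. Linear adjustment multiplies the variance by 1 − r² and is equivalent to 147/(1 − r²) unadjusted patients. The documents do not give r; the range 0.3 to 0.6 is an assumption.

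| r | Variance factor 1 − r² | Variance cut | 95% half-width (SD) | Equivalent N |
|---|---|---|---|---|
| 0 | 1.00 | 0% | 0.343 | 147 |
| 0.3 | 0.91 | 9% | 0.327 | 162 |
| 0.4 | 0.84 | 16% | 0.314 | 175 |
| 0.5 | 0.75 | 25% | 0.297 | 196 |
| 0.6 | 0.64 | 36% | 0.274 | 230 |

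The equivalent gain in patients runs from 1/0.91 = 1.10 (10% more) to 1/0.64 = 1.56 (56% more).

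**3. Gain if the correlation holds on the log scale.** For lognormal costs with log-SD s and log-scale correlation ρ, the raw-scale correlation is (exp(ρs²) − 1)/(exp(s²) − 1). With s = 1.0 this turns 0.3 into 0.20 and 0.5 into 0.38. With s = 1.5 it turns them into 0.11 and 0.25. A simulation of 20,000 trials at 49:98 with no arm effect, using raw or log prior cost as covariate and s of 1.0 or 1.5, gave these cuts in the variance of the mean cost difference:
- ρ = 0.3: about 2-5%
- ρ = 0.5: about 8-17%

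The lognormal form and both values of s are assumptions. The percentages are approximate.

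**4. Chance imbalance.** With no stratification, mean prior cost in the two arms differs by chance with SD 0.175, so the 95% range is ±0.343 SD of prior cost. Carried to the outcome, an imbalance at that limit shifts the unadjusted difference by r × 0.343: 0.10 SD at r = 0.3 and 0.21 SD at r = 0.6. This is the same loss as in step 2 seen in a single trial. The unadjusted SE already includes it, so the two must not be added.

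**The case against.** Several stronger readings are tempting, and the documents do not support them.

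**That usable prior costs are already promised.** The Resources entry is one item in a list beside patient population and demographics. It does not say the costs are patient-level, linked to participants or cover a given period; they could be aggregate planning data. The pre-treatment time point is firmer but generic: the same schedule line covers adherence, which cannot exist before treatment. Section 4.5 recruits from several clinics and practices, and nothing says every participant has CMO records. This objection stands, and confirmation must come before the change.

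**That the named tests cannot use baseline.** Section 5 does not say two-group. ANOVA could be repeated-measures, and either test could be run on change scores. The supportable statement is that use of baseline is left unspecified.

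**That the cost comparison is biased, or that chance imbalance is a further problem.** Randomisation makes the unadjusted comparison unbiased, and a valid SE covers the imbalance.

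**That a gain of 9% to 36% is established.** It needs an assumed correlation on the raw scale. Two features of the plan could lower that correlation. Eligibility removes some patients with high recent cost (recent injections or physical therapy, cardiac admissions, COPD exacerbations). Follow-up cost also contains the allocated therapy itself, which prior cost need not predict.

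It is also fair to say that a general rule adjusting every outcome for its pre-treatment value would nominally cover cost. It would still leave the look-back window undefined, and it would not supply a mean difference on the rank-test branch.

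**Conclusion.** The point holds as an omission. The plan gives cost a pre-treatment time point and names historical costs as a data resource, but specifies no use of either in the comparison. On the skewed branch of Section 5 it would not estimate the mean cost difference that its rationale calls for.

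The second part needs only that cost be skewed, which is an expectation from the components rather than a figure in the documents. The first part is a loss of precision whose size is uncertain: 9% to 36% of the variance for an assumed raw-scale correlation of 0.3 to 0.6, and about 2-5% at 0.3 or 8-17% at 0.5 if the correlation is on the log scale. Both parts of the remedy that use prior cost depend on patient-level records existing.

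This is a low-to-moderate priority improvement to a secondary outcome for which no power is claimed. A reader might infer that the trial's main result is at risk; it is not, because the primary WOMAC comparisons do not use cost.

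**What to change.** First, the sponsor confirms whether the historical or CMO costs are patient-level, can be linked to participants, and for what share of them.

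If so, add to Section 5, before outcome data are seen:
- Define the outcome as cumulative cost from entry to 52 weeks, and state one fixed look-back window for prior cost, for example the 12 months before entry.
- Compare arms by regression of 52-week cost on arm and pre-entry cost. Report the adjusted mean difference with a bootstrap or robust 95% interval, whatever the skewness.
- Do the same for total physician visits, with pre-entry visits as covariate.
- For patients without prior records, use a missing indicator. This is acceptable for a baseline covariate in a randomised comparison.
- Tabulate prior cost by arm.

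If linked prior costs do not exist, drop the covariate but keep the mean difference and its bootstrap or robust interval.

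The cost is a few sentences of analysis text, the choice of a window, and one data extract. The budget already carries 100 hours of informatics, 100 hours of biostatistics and 0.5 FTE of CMO staff. The downside is small provided most participants have prior records; the gain shrinks as that share falls.
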